6.3.3.2 Serious Adverse Event

A serious adverse event is any untoward medical occurrence that:

- Results in death
- Is life-threatening
- Results in persistent or significant disability/incapacity
- Results in a congenital anomaly or birth defect, or
- Requires non-illness or injury related (presenting condition) inpatient hospitalization or prolongation of existing hospitalization (hospitalization for treatment /observation/examination caused by an adverse event is considered to be a serious adverse event)

Important Medical Events:

Important Medical Events are defined as events that:

- may not result in death
- may not be life-threatening
- may not require hospitalization

These may be considered serious adverse, based upon appropriate medical judgment. These events may jeopardize the patient or subject and may require surgical intervention to prevent one of the outcomes listed in this definition (21 CFR 312.32)

6.3.3.3 Reporting

Any serious, adverse event will be reported immediately to the Institutional Review Board.

7. DATA ANALYSIS AND STATISTICAL METHODOLOGY

7.1 Planned Sample Size

Since this is a prospective, efficacy and safety trial, the planned enrollment is for 25 patients who will receive a single dose of intranasal ketorolac. This sample size provides 80% power to demonstrate that the mean pain intensity to demonstrate that the mean pain intensity difference (PID), (where the PID = post-treatment NRS – baseline NRS) differs from zero when the effect size is 0.56. The effect size was calculated as the mean PID divided by the standard deviation.

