5.1.4.2 Study Pain Assessments

Study pain assessments will be done before and after the administration of the single dose of intranasal ketorolac (sprix). All patients will have a minimum of two pain scores (NRS): a baseline (pre administration of the intranasal ketorolac) and a post administration of intranasal ketorolac. The time that the pain score is done, whether at baseline or post intranasal administration of the ketorolac, will be recorded any time a baseline or post-treatment NRS pain score is done. A post-treatment NRS pain score will be done immediately prior to the patient leaving the ED and immediately prior to the patient receiving rescue medication (e.g. any additional pain medication or sedatives) with the time post-treatment to be recorded. Depending on the length of time the patient is in the ED, additional NRS pain scores will be done, if possible. While the patient is in the ED, additional NRS pain scores will be recorded at specified times after study drug administration; specifically, at 20 minutes, 40 minutes, 1 hour, 2 hours, 3 hours, 4 hours, 5 hours and 6 hours for as long as the patient remains in the clinical site, in addition to time 0 (baseline = before administration of the study drug). (See Appendix 1) The pain scores will be compared and analyzed for statistical significance comparing the baseline (pre-study drug administration) with the "post-study drug administration or "treatment" pain scores.

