5.1.6 Efficacy Assessments

5.1.6.1 Pain Assessments

Pain scores will be recorded and documented before administration of the intranasal ketorolac (sprix) for a baseline pain assessment and at specified intervals after the administration of intranasal ketorolac (sprix). Post-treatment pain scores will be recorded immediately prior to discharge from the ED and immediately prior to any rescue (e.g. pain or sedative) medication. Post treatment pain scores will be collected for as long as the patient is in the clinical site and will be at 20 minutes, 40 minutes, 1 hour and for 1 hour intervals post treatment up to 6 hours (e.g. at 1, 2, 3, 4, 5, and 6 hours) in addition to pain scores immediately prior to rescue medication and immediately prior to discharge from the ED. Pain assessments will be by the Numeric Rating Scale (NRS).where 0 = no pain and 100 = the worst pain imaginable. (See Appendix 1)

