5.3 Study Withdrawal Criteria

5.4 Discontinuation of Study Treatment/Early Release from the Study

A subject who is enrolled in the study and for whom study treatment is prematurely terminated will be considered to be discontinued from study treatment. After discontinuation/early release from the study, the subject will receive standard-of-care treatment as per the treating clinician. End of Study Efficacy and Safety assessments will be performed, if appropriate and whenever possible.

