5.6 Noncompliance/Replacement

Subjects who discontinue from the study prematurely will not be replaced.

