7.2 Efficacy

The pain scores pre and post-treatment (after administration of the intranasal ketorolac [sprix]) will be compared. Pain scales are a continuous variable. Therefore, pain scales and other pain assessments (such as PID, SPID) (all continuous variables) will be compared using t-test or F-test.

The questionnaires (patient and health care provider) are discrete variables and will be compared using chi-square or Fischer's exact test.

Significance is at $p=0.05$.

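### The 80% power stated for 25 patients at effect size 0.56 is a normal-approximation figure; the planned t-test (or equivalent 1-df F-test) has 76.6%

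*Combined protocol and SAP*

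**What the plan says.** Section 7.1 (Planned Sample Size) enrols 25 patients in a single arm and gives the plan's only power statement: "This sample size provides 80% power to demonstrate that the mean pain intensity" difference "differs from zero when the effect size is 0.56". It defines that quantity as follows: "The effect size was calculated as the mean PID divided by the standard deviation". This is a one-sample (paired) setting. The section does not name the test, the alpha, the sidedness or the formula behind the 80%.

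Section 7.2 (Efficacy) supplies the test and the level. PID and the other continuous pain measures "will be compared using t-test or F-test", with significance at 0.05. No test that treats the standard deviation as known is planned anywhere.

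On the number of scores available, Section 5.1.4.2 requires at least a baseline and one post-dose score for every patient. Section 5.1.6.1 adds: "Post-treatment pain scores will be recorded immediately prior to discharge from the ED and immediately prior to any rescue" medication. Section 5.4 is weaker for early release: "End of Study Efficacy and Safety assessments will be performed, if appropriate and whenever possible". Section 5.6 says: "Subjects who discontinue from the study prematurely will not be replaced". Section 8 ends the study once 25 are enrolled. No loss rate is given.

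**The concern.** With 25 patients the standard deviation of PID is estimated on only 24 degrees of freedom. The t-test pays for that estimation through a larger critical value and a heavier-tailed statistic; a normal approximation does not. At this size the difference shows, so a power figure from the approximation overstates what the t-test delivers.

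What is at stake is the accuracy of the one power claim in the plan. A reader will take 80% as the operating characteristic of the analysis in Section 7.2. If the approximation was used, the risk of a false negative at the stated effect is higher than reported, and there is no margin to absorb it: enrolment stops at 25, patients who discontinue are not replaced, and no allowance for missing scores is stated.

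**Working it through.** **Inputs**

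- n = 25, single arm (Section 7.1)
- Effect size d = mean PID / SD = 0.56 (Section 7.1)
- Alpha = 0.05 (Section 7.2)
- Test: t-test or F-test (Section 7.2), taken as one-sample on PID because Section 7.1 compares mean PID with zero
- Two-sided: an inference from the wording of Section 7.1, which speaks of differing from zero
- All 25 patients evaluable

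**Step 1. Reproduce the stated 80%**

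Two-sided normal approximation: power = Φ(d√n − z₀.₉₇₅).

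- d√n = 0.56 × 5 = 2.80
- 2.80 − 1.960 = 0.840, and Φ(0.840) = 0.7996
- Required n = ((1.9600 + 0.8416) / 0.56)² = (2.8016 / 0.56)² = 25.03
- Effect size for 80% power at n = 25: 2.8016 / 5 = 0.560

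All three agree with Section 7.1.

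**Step 2. Power of the planned test**

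One-sample t-test, two-sided 5%: power = P(|T| > t₀.₉₇₅,₂₄), where T is noncentral t with 24 df and noncentrality 2.80.

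- Critical value t₀.₉₇₅,₂₄ = 2.064, against 1.960 for the normal
- Power = 0.7662

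F-test of mean PID = 0: noncentral F with 1 and 24 df and noncentrality 25 × 0.56² = 7.84. Power = 0.7662, identical because this F statistic is the square of t. Simulating 4,000,000 normal samples of 25 gave 0.7663.

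Shortfall: 80.0 − 76.6 = 3.4 points. Chance of missing the effect: 100 − 76.6 = 23.4%, against the 20% implied.

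**Step 3. Can another reading rescue the 80%?**

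| Reading (n = 25) | Power |
|---|---|
| t-test, two-sided, d = 0.555 (lower rounding limit) | 75.9% |
| t-test, two-sided, d = 0.56 | 76.6% |
| t-test, two-sided, d = 0.565 (upper rounding limit) | 77.4% |
| t-test, one-sided 5%, d = 0.56 | 85.9% |
| Normal, one-sided 5%, d = 0.56 | 87.6% |
| Normal, two-sided, d = 0.56 | 79.96% |

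Of these, only the two-sided normal approximation gives 80%.

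**Step 4. What would give 80% with the two-sided t-test**

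- At n = 25: d = 0.584 (0.58 gives 79.5%)
- At d = 0.56: n = 27 gives 79.98% and n = 28 gives 81.5%

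**Step 5. Fewer evaluable patients (illustration only)**

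The documents give no loss rate. If n were 24 the power at d = 0.56 would be 74.8%; if n were 22, 70.7%.

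**Side point on sign.** Section 7.1 defines PID as post-treatment minus baseline, so pain relief gives a negative mean while the effect size is written as positive. Two-sided power at −0.56 is the same 76.6%, so this does not affect the result.

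**The case against.** The strongest reply is that nothing was miscalculated. The normal approximation is a standard sample-size tool, 80% is its correct output for these inputs, and Section 7.1 never claims an exact t-test calculation. That stands as an explanation of where the figure came from. It does not make the figure right for the test in Section 7.2, and Section 7.1 presents 80% without calling it approximate.

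A second reply is that Section 7.1 leaves sidedness and evaluable numbers open, so other routes to 80% exist. A one-sided 5% t-test has 79.8% power with 21 evaluable patients and 81.5% with 22, so 25 enrolled with a loss of 12% to 16% (3/25 to 4/25) would come close. This shows that the normal approximation is the most likely source, not the only conceivable one. But that route needs a one-sided test and a loss allowance, neither of which the plan states, and the hypothesis in Section 7.1 reads as two-sided.

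Third, the F-test in Section 7.2 might mean a repeated-measures test over the scheduled times, up to eight post-dose scores. The power of such a test cannot be computed from the documents. The 76.6% therefore applies to the 1-df F-test of mean PID = 0, which is the hypothesis Section 7.1 powers.

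Finally, the practical effect is small. No decision or stopping rule depends on the figure, Section 7.1 gives no source for 0.56, and Sections 5.1.4.2 and 5.1.6.1 make a missing post-dose score unlikely (Section 5.4 supports this only weakly). All of that is fair and limits the point to a minor one.

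**Conclusion.** The concern holds and is minor. For 25 evaluable patients, effect size 0.56 and a two-sided 5% one-sample t-test or its 1-df F equivalent, power is 76.6%, not 80%. Expressed as an effect, the size detectable with 80% power is about 0.584 rather than 0.56.

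This rests on four readings: the test is two-sided, it is one-sample on PID, any F-test is the 1-df test of mean PID = 0, and all 25 patients have a baseline and a post-dose score. Any missing score would lower the power further. The choice of test, endpoint and sample size is not in question.

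**What to change.** Replace the power sentence in Section 7.1 with wording such as:

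> With 25 evaluable patients, a two-sided one-sample t-test on PID at alpha 0.05 has 77% power for an effect size of 0.56, or 80% power for an effect size of about 0.584.

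This also supplies the test, alpha and sidedness that the section now omits. Label any power quoted for fewer evaluable patients as an assumption, since no loss rate is stated. In the same edit, either give the effect size as a magnitude or define PID as baseline minus post-treatment, so that the sign agrees with the 0.56.

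The cost is one sentence and a stated power that falls from 80% to 77%. Nothing else in the design changes.

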7.2 Efficacy

The pain scores pre and post-treatment (after administration of the intranasal ketorolac [sprix]) will be compared. Pain scales are a continuous variable. Therefore, pain scales and other pain assessments (such as PID, SPID) (all continuous variables) will be compared using t-test or F-test.

The questionnaires (patient and health care provider) are discrete variables and will be compared using chi-square or Fischer's exact test.

Significance is at $p=0.05$.

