5.1.6.3 Health Care Provider's Questionnaire(s)

The health care provider questionnaires will be obtained after administration of the intranasal ketorolac (sprix) and prior to the patient leaving the clinical site. (See Appendix 2)

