Appendix 2B: Health Care Provider Questionnaire

1. Was the patient successfully treated (had less pain) by using the spray?
yes __ no __
2. Did the patient have any unacceptable side effects from use of the spray?
yes __ no _____.
3. How satisfied How satisfied were you with the use of the intranasal spray?
Very unsatisfied __ Unsatisfied _____ Satisfied __ Very satisfied _____
4. Would you consider using this intranasal pain medicine in the future for your
patients who have acute pain? yes _____ no _____

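### If one provider answers for several patients, Appendix 2B items 3 and 4 are not independent, yet Section 7.2 tests them as if they were and no provider code is recorded

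*Combined protocol and SAP*

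**What the plan says.** Section 7.1 sets the number of patients: "the planned enrollment is for 25 patients who will receive a single dose of intranasal ketorolac". There is no control arm.

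Section 5.1.6.3 ties the provider form to the visit: "The health care provider questionnaires will be obtained after administration of the intranasal ketorolac (sprix) and prior to the patient leaving the clinical site". Section 5.1.4.3 says the same. One form per patient is therefore implied, although not stated in so many words. Section 6.2.2 makes the provider questionnaire a secondary efficacy variable. Section 2.2.2 lists only PID and SPID under that title.

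Appendix 2B has four items. Items 1 and 2 ask whether this patient had less pain and whether this patient had unacceptable side effects. Item 3 asks "How satisfied were you with the use of the intranasal spray", with four ordered answers. Item 4 begins "Would you consider using this intranasal pain medicine in the future for your" and goes on to the provider's own patients with acute pain, answered yes or no.

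Section 7.2 treats all questionnaire items alike: "The questionnaires (patient and health care provider) are discrete variables and will be compared using chi-square" or Fisher's exact test, at the 0.05 level. It does not say what the answers are compared with.

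Neither Appendix 2B nor the list of study records in Section 9.6 includes a provider identifier. No section gives the number of providers, limits the forms per provider or allows for repeated responders.

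**The concern.** Chi-square and Fisher's exact tests treat each form as a separate, independent answer. For item 4 that is doubtful once a provider has treated two study patients, because the question concerns a standing intention and the second answer is likely to resemble the first. Item 3 shares the problem in part, since a provider's general view of the spray may colour each answer.

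Only one institution's review board is named (Sections 9.2 to 9.5), and the text speaks of the clinical site in the singular. With 25 patients from what appears to be one department, some repetition is plausible.

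What is at stake is how one secondary variable is reported. Section 8 plans a publication. A statement that 20 of 25 providers would use the spray again would be wrong if five people had given those answers. A p-value from 25 supposedly independent answers would also be too small, and a provider with many forms could dominate the result.

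**Working it through.** **The plan's own figure.** Section 7.1 claims 80% power at an effect size of 0.56. With a two-sided 5% level and the normal approximation, n = ((1.960 + 0.842)/0.56)² = 25.03, and power at n = 25 is 79.96%. The figure is reproduced (the exact t-test gives 76.6%). It concerns mean PID only. No precision or power is stated for any questionnaire item, so this point does not touch the sample size.

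**Inputs for the provider items**
- Forms: 25, at one per patient (Section 7.1, with 5.1.6.3).
- Number of providers, k: not in the documents. Assumed 25, 20, 10 and 5.
- Within-provider correlation, ρ: not in the documents. Assumed 0.3 and 0.5.
- Forms are taken as spread evenly. For a given k this is the most favourable case.

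**Formula.** Forms per provider m = 25/k; design effect DE = 1 + (m − 1)ρ; effective n = 25/DE.

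| k | m | DE, ρ = 0.3 | Effective n | DE, ρ = 0.5 | Effective n |
|---|---|---|---|---|---|
| 25 | 1 | 1.00 | 25.0 | 1.00 | 25.0 |
| 20 | 1.25 | 1.075 | 23.3 | 1.125 | 22.2 |
| 10 | 2.5 | 1.45 | 17.2 | 1.75 | 14.3 |
| 5 | 5 | 2.20 | 11.4 | 3.00 | 8.3 |

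For k = 5 and ρ = 0.3, for example: 1 + 4 × 0.3 = 2.2, and 25/2.2 = 11.4.

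**Effect on a test.** The plan names no reference value, so an illustration has to supply one. A one-sample test of a yes/no item against 50% was simulated with beta-binomial answers (200,000 runs per setting). At a nominal 5%, the false-positive rate was 4.3% with 25 different providers. For ρ = 0.3 and 0.5 it was 9.9% and 13.7% with 10 providers, and 18.1% and 25.9% with 5 providers. These rates show direction and rough scale only, because the 50% reference is not the plan's.

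**The case against.** The strongest reply is that the key fact is missing: no section says that any provider answers twice. A reader might infer that precision is certainly overstated. The documents do not support that, because with 25 different providers there is no loss at all. This stands, and the point must stay conditional.

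A reader might also infer that the unit for both items is the provider and that a denominator of 25 is simply wrong. That goes too far for item 3. It follows two questions about the patient just treated and can be read as satisfaction with this particular use, which may differ between one provider's patients. Counting 25 forms is legitimate if they are described as forms. Item 4 is closer to a fixed attitude. Correlations near 1 therefore have no support as a general assumption.

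Nor do the documents show that repeats could never be traced. Appendix 2B gives the question wording, not the whole case report form, and patient charts exist. What can be said is that the plan makes no provision for tracing them.

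It can further be objected that Section 7.2 plans no confidence interval for these items and names no comparator in a single-arm study, so the test is undefined whether or not answers cluster. This is correct and is a separate gap. Naming a comparator would not make repeated answers independent. If the items are only described, no p-value is at risk, but the reader still needs to know how many people answered.

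Finally, the stakes are low: two of four items on one questionnaire, with no success rule attached. That also stands.

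**Conclusion.** The concern holds in conditional form. If the same provider completes the form for more than one patient, answers to item 4, and less strongly item 3, are not independent. Section 7.2 would still test them as though they were, and nothing on the form would show it. The loss is zero with 25 different providers and small with 20. At 5 providers and a correlation of 0.3 to 0.5 it takes the effective number of answers from 25 to about 11 to 8. Provider counts and correlations are assumptions throughout, so no single corrected figure can be given. The NRS and PID analyses, the sample size and provider items 1 and 2 lie outside this point. It is a cheap improvement to the reporting of a secondary variable, not a threat to the main conclusion.

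**What to change.** 1. Add a coded provider number to Appendix 2B, preferably before enrolment, since reconstructing responders from charts later is uncertain.
2. Report the number of providers and the distribution of forms per provider.
3. Amend Section 7.2 so that provider items 3 and 4 are summarised descriptively alongside the provider count, and are not tested as 25 independent answers. A provider-clustered interval or a summary with one answer per provider can be added as a sensitivity summary. Keeping only each provider's last form is one way to do the latter, but it discards data and is not required.
4. Leave items 1 and 2 per patient.

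The cost is one extra field on an existing form and a short amendment to 7.2. The downside is a smaller effective denominator for two items.

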5.1.4.3 Study Questionnaires

Study Questionnaires will be done by the patient and the health care provider after administration of the study drug (intranasal ketorolac [sprix]), prior to the patient leaving the clinical site. (See Appendix 2)

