5.1.6.2. Patient Questionnaires

Patient questionnaires will be obtained after administration of the intranasal ketorolac (sprix) and prior to the patient leaving the clinical site. (See Appendix 2)

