6.2.2 Secondary Efficacy Variables

The secondary efficacy variables are the global pain assessment scores, the global assessment of analgesia (pain relief) scores, the patient questionnaire and the health care provider questionnaire which are completed before the patient leaves the clinical site (e.g. ED).

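### Section 7.2 prescribes chi-square or Fisher's exact tests for post-dose-only questionnaires in a single-arm trial but names no comparison, and patient item 2 cannot record no relief

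*Combined protocol and SAP*

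**What the plan says.** Section 7.2 (Efficacy) treats pain scores as continuous and compares them before and after treatment. It then turns to the two questionnaires, which "are discrete variables and will be compared using chi-square or" Fisher's exact test, and sets significance at 0.05 for the whole section. It does not say what the questionnaire answers are compared with.

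The rest of the protocol fixes the data these tests would use:

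- **One group.** Section 7.1: "the planned enrollment is for 25 patients who will receive a single dose of intranasal ketorolac". Section 3.3 describes active treatment only.
- **One time point.** Section 5.1.4.3: "Study Questionnaires will be done by the patient and the health care provider after administration of the study drug". Sections 5.1.6.2 and 5.1.6.3 repeat the post-dose timing for each form.
- **Secondary status.** Section 6.2.2 lists among the secondary efficacy variables "the patient questionnaire and the health care provider questionnaire which are completed before the patient leaves the clinical site".
- **The forms.** Appendix 2A, patient item 1, asks yes or no whether pain decreased. Item 2 asks how much, with three answers: mild, moderate or strong decrease. No instruction tells a patient who answered no to skip item 2, and no coding rule is given. Appendix 2B, provider item 1, asks yes or no whether the patient had less pain.

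**The concern.** Used to compare groups, chi-square and Fisher's exact tests need at least two groups; used for goodness of fit, chi-square needs a reference distribution. The plan supplies neither for the questionnaires. If the comparison is chosen after the answers are seen, the p-value tests a hypothesis that was not fixed in advance, and the choice can decide whether the result falls below 0.05.

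Item 2 is a separate fault in the form. A patient with no relief must either leave it blank or tick a degree of benefit. Summarised over those who answered, it can show only benefit. In a nonblinded single-arm trial, which Section 8 says will lead to an abstract and a manuscript, an item of that kind is easily quoted alone.

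**Working it through.** **The plan's own figure.** The only computed figure is in Section 7.1: 80% power with n = 25 at effect size 0.56 for mean PID. By the normal approximation, power = Φ(0.56 × √25 − 1.96) = Φ(0.84) = 0.80, so it reproduces on that basis. It concerns PID only; no figure covers the questionnaires.

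**Step 1: look for a comparison.**

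- Control arm: none (Sections 3.3 and 7.1).
- Baseline: none (Sections 5.1.4.3, 5.1.6.2 and 5.1.6.3). The items ask about a medicine already given, so the pre/post comparison of pain scores cannot carry over.
- Reference proportion or subgroup: none is stated.
- Patient against provider: possible, but not stated. Only item 1 asks both raters about the same thing. Item 2 differs (pain decrease; side effects), and items 3 and 4 ask each rater's own view.

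**Step 2: does an unstated reference matter?** Assume 18/25 yes. Goodness-of-fit χ² = Σ(O − E)²/E on 1 df:

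- against 50%: 5.5²/12.5 + 5.5²/12.5 = 4.84, p = 0.028
- against 60%: 3²/15 + 3²/10 = 1.50, p = 0.22
- against 70%: 0.5²/17.5 + 0.5²/7.5 = 0.048, p = 0.83

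**Step 3: patient against provider on item 1.** Assume 20/25 patients and 14/25 providers answer yes. Stacked as two separate groups of 25, Fisher's test gives p = 0.13. The answers are paired by patient, and these margins allow six sets of discordant pairs (b = patient yes and provider no; c = the reverse; b − c = 6). Exact McNemar, p = 2 × P(X ≤ c) with X ~ Bin(b + c, 0.5):

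| b v c | p |
|---|---|
| 6 v 0 | 0.031 |
| 7 v 1 | 0.070 |
| 8 v 2 | 0.109 |
| 9 v 3 | 0.146 |
| 10 v 4 | 0.180 |
| 11 v 5 | 0.210 |

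The conclusion at 0.05 differs from the stacked Fisher result in one of the six.

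A cross-tabulation answers another question. For 6 v 0 the table is 14 both yes, 6 patient only, 0 provider only, 5 both no. Fisher's p = C(11,5)/C(25,5) = 462/53,130 = 0.009; the opposite extreme table has probability C(14,5)/C(25,5) = 2,002/53,130 = 0.038, which is larger and so adds nothing. That tests whether the answers are associated, not whether the yes rates differ.

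**Step 4: item 2.** Assume 5 of 25 patients have no relief.

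- All five leave item 2 blank: a decrease in 20/20 = 100% of those answering, against 20/25 = 80% of all dosed (Clopper-Pearson 95% CI 59% to 93%).
- All five tick mild: 25/25 = 100%.
- Range: with 2 to 8 blanks, those answering still show 100%, while the share of all dosed runs from 23/25 = 92% to 17/25 = 68%.

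**The case against.** The strongest reply is that a test of association needs two categorical variables, not two arms. Patient item 1 by provider item 1 is such a table, with one independent unit per patient, and Fisher's test is valid on it. This stands. A reader might infer that the planned tests cannot be computed, or that independence fails in every patient-provider comparison. The documents do not support either: pairing is ignored only if the two sets of 25 answers are treated as separate groups, and Section 7.2 states neither layout. What remains is that no comparison is named, and that a cross-tabulation would not test a difference in rates.

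On item 2, the reply is that it reads naturally as a grading question for those who said yes to item 1, and that lack of benefit can also be recorded on patient items 3 and 4, provider item 1 and the global analgesia scale. This also largely stands. A reader might infer that the questionnaire as a whole is biased towards benefit; it is not, because item 1 takes a plain no. The fault is confined to item 2, where no skip instruction is printed.

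A reader might also infer a missing-form problem, because Section 5.4 says that end-of-study "assessments will be performed, if appropriate and whenever possible" and Section 5.6 says "Subjects who discontinue from the study prematurely will not be replaced". The support is thin. Section 5.4 concerns treatment ended prematurely, treatment here is two sprays, and both forms are due before the patient leaves. No missing-form rate can be drawn from the documents.

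**Conclusion.** The point holds at a modest level. Section 7.2 assigns a significance test to questionnaires for which the design supplies no treatment group, no baseline and no reference, and patient item 2 has no answer for no relief.

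The sizes rest on assumed counts. The choice of reference moves p from 0.028 to 0.83 for the same 18/25. Ignoring the pairing changes the 0.05 conclusion in one of six possible tables, so that part is mainly a matter of using the right method. With five patients without relief who leave item 2 blank, it shows 100% of those answering against 80% of all dosed.

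The reach is limited. Section 6.2.2 makes the questionnaires secondary, and Section 2.2.2 does not list them among the secondary efficacy variables at all. The primary NRS analysis and the PID-based sample size are unaffected, and nothing here should be read as a criticism of either.

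**What to change.** In Section 7.2, replace the chi-square/Fisher sentence with: 'Questionnaire answers are reported as counts and percentages of all dosed patients, with an exact 95% CI for the yes/no items; no between-group p-value is given. If patient item 1 and provider item 1 are compared, the exact McNemar test is used.'

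In Appendix 2A, add 'No decrease in pain' to item 2. If forms are already in use, report patients who answered no on item 1 and left item 2 blank as 'no decrease', and list any contradictory answers, such as no on item 1 with mild ticked on item 2.

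The cost is two sentences and one tick-box or coding rule, with no extra patients or visits. The yes/no items number five (patient 1 and 4; provider 1, 2 and 4), so five intervals are needed. The downside is that these secondary items carry no between-group p-value, which the single-arm design could not support in any case.
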